---

## DOCUMENT HISTORY

VERSION	DATE	REASON OF CHANGE

---

## 1. PROTOCOL SYNOPSIS

ADMINISTRATOR	CHU de La Réunion – Site of GHSR
RESEARCH RESPONSIBLE	[name] PH Algology Responsible of Chronic Pain Service Group of Hospital South Réunion University Hospital Centre of Reunion
TITLE	Prophylactic effect of music therapy on episodic migraine patients under the care of chronic pain department.
VERSION	1.0
JUSTIFICATION / CONTEXT	Music therapy has been validated in the management of chronic pain and anxiety disorders. A program of music therapy will be proposed by the CHU Chronic Pain department team from GHSR. The objective of this study is to evaluate the effect of the music in the migraine specific indication.
OBJECTIVES	
Principal objective To evaluate the effect of music therapy on migraine frequency, on patients suffering from episodic migraines and followed in chronic pain department of the CHU Sud Reunion.
 
Secondary objectives To evaluate the effect of music therapy on migraine intensity, duration, and acute treatment administration. To evaluate the effect of music therapy on emotional effect (HAD score) and functional impact (HIT-6 score).

STUDY DESIGN	Prospective study of before-after type. It is composed of only one group of patients, all treated with music. The study will measure and compare migraine frequency in the month before the intervention with data collected 3 months after.
INCLUSION CRITERIA	
 
- patients aged <math>\geq 18</math> years
 
- patients with episodic migraine (<15 days / month) with at least 4 crises per month.
 
- patients with migraines with or without aura with diagnostic criteria per International Headache Society
 
- patients with a migraine for more than one year
 
- diagnosis age < 50 years
 
- patients with an available internet connexion to access Music Care application
 
- patients with minimal knowledge in informatics
 
- patients who sign their inform consent
 

EXCLUSION CRITERIA	
 
- patients aged less than 18 years
 
- patients with chronic migraine
 
- patients with epilepsy
 
- patients with a deficiency on auditive function
 
- patients with a disease that could be fatal within the study period.
 

STANDARD CARE NATURE EVALUATED IN THIS RESEARCH	Sessions of music therapy self-directed by the patient at home, using Music Care software via an internet connexion.
EVALUATION CRITERIA	
Primary evaluation criterion Reduction of migraine frequency of 50% after 3 months.
 
Secondary evaluation criteria Reduction of migraine intensity and duration, as well as acute treatment administration. Reduction of the emotional and functional impact.

PLANNED SAMPLE SIZE	20 patients
PLANNED CENTERS	1 centre: Chronic Pain Department of CHU-GHSR site of Saint-Louis
DURATION OF THE RESEARCH	
 
- Duration of inclusion period: 1 month
 
- Duration of patient participation: 3 months
 
- Total duration of the study: 4 months
 

STATISTICAL ANALYSIS	
Analysis of the primary endpoint The mean number of migraine crises per month before and after music therapy will be compared using the Wilcoxon Paired Test.
 
Analysis of secondary endpoints Quantitative variables before and after music therapy will be analysed using Wilcoxon Paired Test. Qualitative variables will be analyzed using McNemar Chi test.

EXPECTED RESULTS	
To propose a new therapeutic and non-drug approach in episodic migraine prophylaxis.
 
To improve the relationship between medical team and patients.
 
To reduce the treatment consumption.

## 2. SCIENTIFIC JUSTIFICATION

Migraine is a frequent pathology, it affects 20% of the French population and represents 1 milliard euros of direct cost. It is a research topic largely studied under non-drug approaches. The ANAES provided in its migraine recommendations in October 2002 to use relaxation, biofeedback and stress management cognitive and comportemental therapies in the care of migraine patients.

Music therapy is a recent discipline with a trend of development in hospital services and in specialised ambulatory care centres. Several controlled studies allowed to validate the utilisation of music therapy in chronic or sharp pain, as well as in anxio-depressive disease. In this domain, the work of [name], psychologist and music therapist, helped using Music Care software to elaborate a standardised computerised method allowing its use by caregivers and patients themselves.

Researches on music therapy effect on migraine patients are few.

A first German study in 1999 evaluated the effect of *Psychophonia* software on migraine, informatic tool which build a sound sequence from EEG of the patient. This cohort study on 55 adult migraine patients showed a decrease of at least 50% of migraine crises in 56% of patients treated for 12 months.

A second German study in 2008 evaluated the effect of active music therapy and the use of butterbur root extract (Petalodex) in the prevention of child migraine. This randomised, controlled study based on 58 patients distributed under 3 arms (music therapy/ butterbur/placebo) demonstrated superiority of music therapy arm against placebo after 8 weeks, and the superiority of the 2 treatments against placebo at 6 months.

The demonstrated effects of music therapy on chronic pain and anxio-depressive disease allow to assume a benefic effect of this technique in the migraine.

Scientific data of music therapy on migraine patients are positive and suppose its interest in this indication, as in chronic pain, but additional and more specific studies are needed to evaluate its indication on this specific pathology. A clinical study with 2 arms might be helpful.

The standardised and validated music therapy technique named as *Music care* seems to be a useful tool in standard cares and clinical research.

### 2.1. CURRENT STATE OF KNOWLEDGE

#### 2.1.1.ON THE PATHOLOGY

Episodic migraine is defined as several days with crisis < 15 days / month.

Its prevalence is equal to 12% to 20% in the general French population, so 7 million of migraine patients, with more women (ratio of 1/3).

This pathology starts before 40 years with high anxio-depressive comorbidity due to possible pathophysiologic community.

It is an under-diagnosed pathology, with only 30% of migraine followed patients.

The disease consequences are functional disability, current activities reduced in 70% of migraine patients.

The social impact cost is estimated to 1 milliards euros / year and 15 million of loosed days of work / year.

Fifty percent of the patients used auto medication with a risk of drug abuse and evolution to chronic migraine (> 15 days of crisis / month).

#### 2.1.2.ON THE STRATEGIES/REFERENCE PROCEDURES

Recent clinical and neurophysiological studies made it possible to highlight the positive effect of music therapy in pain treatment. Causing relaxation, music decreases painful phenomena in patients with

chronic and sharp pain. By shifting the attention, music decreases muscular tension and reduces anxiety. In pre and postoperative pains, patients under music decreased their drug consumption up to 30%. The effects of music therapy are generally related to the fact that the individualized music broadcasting improves interactive components of pain. The impact of music therapy might be due to neurophysiologic effects, specific to pain, and to the music effect on sensory (attenuation of the conduction of afferent fibres), cognitive (memory encoding, diverts attention), affective (stimulates the production of endorphins) and behavioural (psychomotricity, muscular hypertonia) components. The effect of the music therapy is based on the impact of music on the components of the painful experience and the modification of pain perception.

Psychological factors can interfere in the reduction of chronic painful phenomenon: music is chosen by the patient with his personal preferences, it allows to respond to an individual listening request. Listening to the patient after the music session allows him to evacuate their tensions.

Several controlled studies demonstrated that receptive music therapy and more specifically psychomusical relaxation has an efficacy on several painful pathologies like dental, obstetrical, cancerous, chirurgial, neurological, rheumatic and et functional. 

## **2.2. RESEARCH HYPOTHESES**

The study is based on the hypothesis of a prophylactic effect of music therapy on migraine disease using its action on the 4 components: sensory, affective, behavioural and cognitive.

## **2.3. NATURE OF STANDARD CARES EVALUATED IN THE RESEARCH**

Music therapy sessions are based on the use of Music Care software. It is software developed by the music therapist psychologist [name]. Ten services in CHU GHSR will be equipped of it and their teams will be trained to it under the framework of the institutional training plan. This project has been proposed by [name] responsible of Chronic Pain Department GHSR and supported by CLUD GHSR.

Among concerned services, Chronic Pain Department GHSR will propose standard cares by music therapy for chronic migraine patients.

## **2.4. JUSTIFICATION OF METHODOLOGIC CHOICES**

This study has been designed as a before-after study without control group. Intervention being realized under current practice, it will not be possible to propose a randomised trial with one arm is treated with music therapy and another one not.

The month before inclusion will serve as reference. Effect of music therapy will be evaluated during 3 months after inclusion, using a period of same duration of the reference one and using the same tools.

During the 3 months, patients will be followed every month during a visit realised at Chronic Pain Department of GHSR in order to evaluate if the patient is compliant in completion of migraine diary, uses correctly Music Care and if he is compliant with his program. During the visit, migraine evaluation will be evaluated.

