### 7.1. PRIMARY ENDPOINT

**Reduction of migraine crisis frequency of at least 50% after 3 months of treatment.**

The studied variable will be the monthly frequency of migraine crisis. Data collection will be done using a migraine agenda (annex 1), starting the month before inclusion and music therapy initiation. This agenda

should then be completed usually during study period under music therapy. During each monthly visit, a control will be done by the intern of general medicine associated to the study.

The primary endpoint will be obtained using the difference between mean crisis frequency during the month before music therapy initiation and the one obtained during the 3rd month of treatment.

A reduction of at least 50% at month 3 will be considered as music therapy efficacy on episodic migraine prevention.

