## 7.5. SCREENING VISIT

Screening visit will be managed by the algologist responsible of the study. It will be done between 4 months and 1 month before inclusion visit.

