## 7.6. INCLUSION VISIT

During this visit, a complete information on objectives and course of the study is provided to the patient. Informed consent is collected by the algologist investigator of the study.

Diagnosis questionnaire, and HAD and HIT questionnaires HAD et HIT are completed with the investigator. Migraine agenda to be filled during the next 3 months is provided to the patient.

A training to *Music care*, music therapy software, is realized by the study responsible. Details on methodology, objectives of the technique, as well as the optimal conditions of use are given to the patient. During this visit, the first music session is done at the hospital under medical control. A questionnaire is filled in order to have a better knowledge of migraine patient about music preferences likely to bring him to relaxation.

A secure account is created to allow patients to have a free internet access and use *Music care* during the study.

At the end of this visit, the patient should be able to use at home by himself the software and to realize music therapy sessions using *Music care*.

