## 7.7. FOLLOW-UP VISITS

Follow-up visits will be monthly done by the investigator, at Month 1, Month 2 and Month 3 after inclusion. During these visits, checks will be done regarding agenda migraine completion, patient motivation will be evaluated, and the number of music sessions done will be collected.

Impressions and feeling of the patient regarding music sessions will be collected.

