3.1. PRIMARY ENDPOINT

Reduction of migraine crisis frequency of at least 50% after 3 months of treatment.

The studied variable is the monthly frequency of migraine crisis. Data collection is done using a migraine agenda (annex 1 of protocol), starting the month before inclusion and music therapy initiation. This agenda should then be completed usually during study period under music therapy. During each monthly visit, a control will be done by the intern of general medicine associated to the study.

The primary endpoint is obtained using the difference between mean crisis frequency during the month before music therapy initiation and the one obtained during the 3rd month of treatment. A reduction of at least 50% at month 3 is considered as music therapy efficacy on episodic migraine prevention.

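### A Month 3 fall of at least 50% is labelled music therapy efficacy, but a single-group before-after design cannot attribute the fall to music

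*Protocol*

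**What the plan says.** Protocol section 2.4 is open about the design: "This study has been designed as a before-after study without control group". The reason given is that music is delivered under current practice, so that "it will not be possible to propose a randomised trial with one arm is treated with music therapy and another one not". SAP section 1 repeats both statements.

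The primary endpoint section then ties a conclusion to the result. Protocol section 7.1: "A reduction of at least 50% at month 3 will be considered as music therapy efficacy on episodic migraine prevention". SAP section 3.1: "A reduction of at least 50% at month 3 is considered as music therapy efficacy on episodic migraine prevention". Neither document qualifies this for natural course, expectation or extra care.

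The formal analysis (Protocol section 9.2, SAP section 5.2) is a paired Wilcoxon signed rank test of the month before music against Month 3. It tests for any change, not for a 50% change.

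The two periods differ in care as well as in music. At the inclusion visit (section 7.6) patients are trained, and "During this visit, the first music session is done at the hospital under medical control". Monthly follow-up visits come next, at which diaries and sessions are checked and "patient motivation will be evaluated" (section 7.7). In the reference month the patient only keeps a diary.

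**The concern.** The primary objective is the effect of music therapy on migraine frequency. In one group measured twice, the observed change is the sum of any music effect and everything else that differs between the two months: the course of the disease, expectation, training, the supervised session and the monthly contact. Section 2.4 matches the two periods on length and measuring tools. That makes the measurements comparable, but not the care.

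With no concurrent comparison, nothing in the data separates these parts. A sentence that names the whole change as efficacy of music therefore claims a property the design does not have. Because it stands in the endpoint definition of both documents, it would pass directly into the report.

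**Working it through.** **The plan's own figure.** Protocol section 9.1 and SAP section 5.1 give a baseline mean of 8 crises per month, SD 4, a 50% fall (8 to 4, so a difference of 4), power 90%, alpha 5% and 20 patients. The paired formula is n = (SDdiff × (z_alpha + z_power) / 4)², with SDdiff = 4√(2(1 − rho)). The documents state neither rho nor sidedness. Two-sided with rho = 0: (5.66 × 3.24 / 4)² = 21.0, so 22. With rho = 0.05: (5.51 × 3.24 / 4)² = 19.9, so 20. The figure of 20 can be reached and is not in question here.

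**Model with no music effect.** Patient rates are gamma with mean 8 and variance 8; monthly counts are Poisson. Total variance is 8 + 8 = 16, so the SD is 4, as in the plan. The Month 3 rate is (1 − f) times a patient rate, where f is a fall from non-specific causes. The documents give no value for f, so 10 to 40% is an assumption. Two extremes are used: the same patient rate in both months, or independent rates. There are 20 patients, 2,000 or more simulated trials per setting, and a two-sided Wilcoxon test at 5%. With f = 0 the test shows a significant fall in about 2% of trials, as it should.

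| Assumed non-specific fall | Wilcoxon significant, with a fall | Group mean falls by at least 50% | Patients whose own count falls by at least 50% |
|---|---|---|---|
| 10% | 8–14% of trials | about 0% of trials | 18–24% |
| 20% | 23–42% | about 0% | 24–30% |
| 30% | 50–77% | 0.5–2.5% | 33–37% |
| 40% | 79–96% | 9–15% | 44–45% |

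In the Wilcoxon column the upper end belongs to identical patient rates. In the other two columns it belongs to independent rates. Repeat runs move the entries by about a percentage point.

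**Hand check of the Wilcoxon column.** Take a paired t-test, n = 20, a non-specific fall of 2 crises (25% of 8) and rho = 0.5. Then SDdiff = 4, the noncentrality is 2 / (4/√20) = 2.24, and the chance of p < 0.05 is 56%. Across rho from 0 to 0.7 it runs from 32% to 78%.

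**Hand check of the 50% column at f = 40%.** The group mean halves when the mean of (Month 3 count − half the baseline count) is zero or less. Its expectation is 4.8 − 4 = 0.8.
- Independent rates: variance = 0.36 × 8 + 4.8 + 0.25 × 16 = 11.68; standard error = √(11.68/20) = 0.76; z = 1.05; probability about 15%.
- Same rates: subtract the covariance term 0.6 × 8 = 4.8, leaving 6.88; standard error 0.59; z = 1.36; probability about 9%.

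**Are such falls plausible?** The documents cannot say. One contributor can be illustrated. Suppose the month used for selection (at least 4 attacks, under 15 days) were also the baseline month. Then an assumed normal parent population (mean 5 to 7, SD 4.5 to 5, rho 0.3 to 0.7) gives a fall of about 0.4 to 1.9 crises from regression to the mean alone. This is only indicative: the selected SD in that model is about 2.8, not 4. The documents also place the eligibility check both at screening (Protocol section 7.5.1) and at inclusion (section 5.3).

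**The case against.** The design is disclosed in the synopsis, in sections 2.4 and 4.1 and in SAP section 1, and the 50% threshold is taken from the national recommendation cited in section 7. The criterion that carries the efficacy label is also demanding. Read as a fall in the group mean, it is almost never met through non-specific falls of 30% or less. All of that stands. It limits how often the label would be applied wrongly, but it does not make the label a statement about music. The recommendation gives a rule for judging whether a treatment is working; it does not supply a comparison.

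Three stronger readings are tempting, and the documents do not support them.

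- *That the high Wilcoxon percentages show how often efficacy would be falsely declared.* The efficacy wording is attached to the 50% reduction, not to p < 0.05. The percentages show only that the formal test gives no protection against non-specific change.
- *That the wait before music contradicts section 2.4.* Section 7.5 says of screening: "It will be done between 4 months and 1 month before inclusion visit". This is a scheduling window around a one-month diary run-in, and every patient passes through it. Section 2.4 rules out only a randomised trial of music against no music, and a visit window does not refute that. Nor does the study account created at inclusion (section 7.6) show that music would otherwise be unavailable.
- *That the wait could simply be randomised.* Waiting patients would have none of the training, supervised session or monthly visits, so contact and expectation would remain confounded with music. With 10 against 10, power is 61–88% for a difference of 4 crises and 20–35% for a difference of 2 (rho 0 to 0.7, baseline-adjusted). It would also change when treatment starts, and it does not fit the stated 3-month participation and 4-month total.

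**Conclusion.** The point holds for the wording of the conclusion. Protocol section 7.1 and SAP section 3.1 attribute to music a fall that a single-group before-after design cannot attribute to anything in particular.

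The size depends on which rule is used and on the assumed non-specific fall. At 20%, the Wilcoxon test would be significant in about a quarter to two-fifths of trials with no music effect, and the group mean would almost never halve. At 40%, the mean would halve in about 9–15% of trials. If the 50% is meant per patient, between roughly a fifth and just under half of patients would meet it without any music effect. The plan does not say which reading applies. These figures rest on the gamma-Poisson model and the assumed falls.

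The point does not show that the study should have been randomised, or that the sample size is wrong.

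**What to change.** In Protocol section 7.1 and SAP section 3.1, keep the 50% criterion but replace the statement that meeting it is efficacy with: *reported as the before-after change during the music therapy programme; not attributable to music alone*. Use the same wording in the report.

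This costs no patients, visits or analyses. The downside is a narrower claim.

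Separately, reconcile the timing statements. Section 7.4 labels screening M-1, section 7.5 allows 1 to 4 months before inclusion, and the synopsis and section 7.3 give a total study duration of 4 months. A patient screened 4 months before inclusion and followed for 3 months would span 4 + 3 = 7 months.

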## **3. OBJECTIVES**

### **3.1. PRIMARY OBJECTIVE**

To evaluate the effect of music therapy on migraine frequency, on patients suffering from episodic migraines and followed in chronic pain department of the CHU Sud Reunion.

### 3.2. SECONDARY OBJECTIVES

- To evaluate the effect of music therapy on migraine intensity, duration, and acute treatment administration.
- To evaluate the effect of music therapy on emotional effect (HAD score) and functional impact (HIT-6 score).

## 4. STUDY DESIGN

### 4.1. METHODS

Monocentric, prospective before-after study.

It comprises of only one group of patients and all of them will receive the intervention.

The study will measure and compare migraine frequency during the month before inclusion with migraine frequency 3 months after the inclusion.

- **Entry in the study:** based on proposition of algologist doctor involved in the patient care and after patient receives information and signs inform consent.

- **Inclusion period:** the month before the initiation of music session will serve as reference period. Patient will fill migraine diary, complete questionnaires on functional and emotional impact used usually in the department.

The following endpoints will be evaluated:

- migraine severity (number of days with migraine, duration, intensity, treatment)
- questionnaire HAD to evaluate emotional impact
- questionnaire HIT to evaluate functional impact

#### - **Music therapy session implementation**

Each patient will be asked to follow 1 to 2 sessions per day for 3 months, to be done at home, using *music care* software via internet connexion.

They will complete the migraine diary during the 3 months of the study.

They will have a visit at the Chronic Pain Department every month, so at Month 1, 2 and 3, realised by an intern of general medicine.

#### - **Final evaluation at Month 3**

Diary data of the third month will serve for this evaluation according to the guidelines of the International Headache Society:

- number of days with migraine (primary endpoint)
- duration and intensity of migraine
- medication consumption
- emotional impact: score HAD
- functional impact: score HIT.

